4.2 Sample Size

Data from two preliminary studies at MOI inform our projection for requisite statistical power. Our pilot study showed a difference in reoperation rate comparing external fixation and intramedullary nailing of 38% versus 3.8%, respectively. However, with longer follow-up and more stringent criteria for reoperation, we estimate a more conservative effect size is needed for power analysis. Therefore, to achieve 80% power (alpha=0.05) with a more conservative difference in the reoperation rate of 5% to 20%, the study would require 88 patients in each treatment group, or a total of 176 with completed follow up.

During the six month period from January to June 2012, MOI surgeons treated 238 patients presenting with open tibia shaft fractures, 50% (119) of whom suffered Gustilo Type 3A injuries - an incidence of approximately 20 patients per month. Our colleagues report the rate of open tibia fractures has continued to increase over the last two years and by current accounting, averages 25 patients with Gustilo Type 3A injuries per month. We therefore estimate an annual volume of approximately 300 qualifying injuries treated operatively at MOI. Assuming the majority meet inclusion criteria and a capture rate of 80%, we anticipate enrolling approximately 240 patients over a one year collection period. If the goal of 80% follow-up is met, a total of 192 patients will be included in our final analysis and we will achieve adequate statistical power. We will plan to conduct an interim analysis after six months to assess the accuracy of these initial estimates and determine whether the duration of the enrollment period should be altered.

4.3 Timeline

November 2015:	Training, refinement, and implementation of study protocol
December 2015:	Begin study enrollment
January 2016:	1 month evaluation and consideration for protocol changes
June 2016:	Site visit for 6 month interim analysis and progress report
December 2016:	End study enrollment and 1 year site visit/interim analysis/progress report
June 2016:	Site visit for 18 month interim analysis and progress report
December 2017:	Complete follow-up data collection
March 2017:	Final data analysis

5. Study Procedures

5.1 Screening

Screening for patients will begin on December 14, 2015 at 9am and end in approximately one year when the appropriate sample size has been reached. All open tibia fractures arriving at the MOI emergency room during the enrollment period will be screened for inclusion in the study. All patients, even those who are excluded, need to have their information recorded on REDCAP.

The orthopedics department has been directed to call the study phone whenever an open tibia patient comes in. The research coordinator is required to keep the study phone close with them at all times.

- If the patient arrives during normal business hours (7am to 5pm), the coordinator will go to the emergency room to assist the patient's physician with screening. The coordinator is also expected to periodically check the emergency room for any new open tibia patients in case the emergency staff fail to contact the study phone.
- The study coordinator on duty will remain at MOI until 9pm and periodically check the emergency room for any new open tibia admissions. If the patient arrives from 9pm to 11pm, the coordinator will screen from home using the study laptop. If the patient meets study inclusion/exclusion criteria, the coordinator will come to the hospital to consent the patient to enroll in the study.

Inclusion Criteria

1. Skeletal maturity
2. AO/OTA 42 open tibia fractures *
3. Wound primarily closeable (no flap or delay in closure due to contamination needed)
4. Palpable pedal pulses (no vascular injury sustained)
5. Presentation within 24 hours from injury **

Exclusion Criteria

1. Current injury is a pathologic fracture
2. Sustained bilateral tibia fracture
3. Sustained comminuted femur fracture
4. Sustained severe Traumatic Brain Injury (GCS<12) ***
5. Sustained severe spinal cord injury (lower extremity paresis/paralysis)
6. Sustained severe burns (>10% total body surface area (TBSA) or >5% TBSA with full thickness or circumferential injury)
7. Prior ipsilateral leg injury requiring surgery
8. Prior or current lower limb deformity or abnormality
9. Unable to complete follow-up visits

* See addendum for OTA42 subclassification schematic

** Patients who present greater than 24 hours after injury and/or have non-primarily closeable wounds but meet all other criteria are eligible for the cohort study (see below)

*** If at any point prior to the operation, the patients GCS score drops below 12, the patient will be excluded from the study. If the GCS score drops below 12 after the operation, the patient will remain in the study.

Cohort Study

Patients who meet all inclusion/exclusion criteria but present to MOI's emergency room beyond 24 hours after their injury and/or have non-primarily closeable wounds will be consented and included in a separate cohort study. These patients will be treated exactly the same way as an RCT patient with the same data collected except that they will not be randomized. Their primary surgeon will decide which operation is the most appropriate. The same consent form will be used, but the patient will be explained the details of the cohort study rather than the RCT study.

Informed Consent

All patients who remain eligible after clinical screening will be offered enrollment in the study. A written informed consent document will be provided to the patient and reviewed in detail by a trained research coordinator. This document will be provided in English or Swahili depending on the patient's preference. In cases where the participant is unable to provide consent, consent will be obtained from a legally acceptable representative. If the participant is unable to read, verbal consent will be provided in the presence of an impartial witness. The consent document should be signed and dated by the individual providing consent as well as the participant or their legally acceptable representative.

Signed consent forms should be kept in the SIGN Nail Office. A picture of the signature form should be taken and uploaded onto REDCAP.

If there is any concern from either the patient and/or the research coordinator that the patient will be unlikely to complete any follow-up visits (especially the 1 year follow-up visit), that patient will be excluded from the study. If the patient does not provide consent for any other reason besides an inability to complete follow-up clinics, the reason for not providing consent will be recorded.

Baseline Clinical Information

Once a participant has completed informed consent, the research coordinator will obtain baseline clinical information and record the information in REDCAP.

Antibiotics Administration

Antibiotics must be administered as close to admission as possible to minimize the risk of infection. The standard study antibiotic regimen is based on the estimated level of contamination. This depends on the clinical history and a visual assessment of the wound. It is up to the discretion of the treating surgeon which antibiotic regimen the patient will be placed on. It is recommended that the surgeon utilize one of the three regimens, but in cases where there is a compelling reason for the use of a non-study regimen, the surgeon is allowed to place the patient on a non-study antibiotic.

The breakdown of the antibiotic regimen only with details regarding whether or not the study will provide the antibiotics can be found below.

Contamination Level	Treatment	Provision Status
None or mild	Ceftriaxone 1g every 24 hr for 2 days	Provided for free

Moderate	Ceftriaxone 1g every 24 hr for 2 days + Gentamycin 80mg every 12 hr for 2 days	First dose gentamycin provided for free. If the patient cannot or is unwilling to pay to complete the regimen, the full course will be provided for free
Severe or high risk	Ceftriaxone 1g every 24 hr for 2 days + Gentamycin 80mg every 12 hr for 2 days + Metronidazole 500mg every 8hr for 2 days	First dose gentamycin and metronidazole provided for free. If the patient cannot or is unwilling to pay to complete the regimen, the full course will be provided for free

For patients who receive additional operations as part of their care (such as definitive treatment following damage control or reoperations), the antibiotics will be provided according to the same system as detailed in the table above.

There are three stages in the study where antibiotics can be administered:

1. Admission to MOI: all study participants will receive antibiotics at admission. The type of antibiotic to administer is based on a visual assessment of the wound as well as the clinical history provided by the patient. The decision to provide antibiotics should be done immediately following consent by the patient. A standard study antibiotic regimen should be administered unless another antibiotic is believed to be more suitable for the situation.
2. After surgical debridement: the study participant's surgeon may order additional antibiotics to be administered after further evaluation of the wound during surgical debridement. These may be standard study antibiotics or can be any other antibiotic that is available in the OR and that the surgeon believes is more suitable for the situation.
3. In the ward: the ward physician must continue the antibiotic regimens that have already been started in stages 1 and 2 and is also free to prescribe any additional antibiotics that may be necessary. These do not have to be from the standard study regimen. This applies primarily to patients who need to stay in the wards longer to recover from other associated wounds.

A system of recording which antibiotics were administered at each of the three steps has been built into REDCAP. The surgeon is allowed to stop a course of antibiotics at any point during the patient's treatment. If that is the case, the details of the situation will be recorded in REDCAP.

5.2 Radiographs

AP and lateral view x-rays should be taken at the following stages of the study: pre-op, post-op, 6 weeks, 3 months, 6 months, and 1 year. Research coordinators should try to be with the patient while these x-rays are taken to ensure that images of adequate quality are taken.

Radiographs are viewable through ClearCanvas enabled MOI desktops which are available in the radiology department, emergency department, and outpatient department.

A picture of the radiographs should be taken and uploaded onto REDCAP. The name of the patient should be visible on the picture taken. A reviewer from UCSF will review the baseline and follow-up x-rays within a reasonable timeframe after the pictures are uploaded.

Preoperative x-rays will be assessed for fracture classification. Follow up x-rays will be assessed for evidence of hardware failure and fracture union, as determined by the RUST score. In cases of disagreement, the reviewers will meet and achieve consensus. All data entry will be performed directly into REDCap.

5.3 Quality Control

To ensure quality of the x-ray, the radiology department has been notified to make sure that the x-rays include the fracture site and as much of the tibia as possible. For tall patients with long tibias, this may not be possible with the cassettes that are currently available for use by the department. If that is the case, 4 x-rays should be taken at each step of the patient's care: proximal tibia AP and lateral views as well as distal tibia AP and lateral views. However, this should be avoided when possible to minimize radiation exposure to the patients. The cost of the extra x-rays will be covered by the study. An option to upload additional x-rays has been built into REDCAP.

Post-op x-rays ideally are performed immediately after surgery. However, sometimes the x-ray department is backed up or the patient is uncooperative. If that is the case, try to notify the ward physician on duty to order the post-op x-rays. While it is under MOI policy that patients should not get discharged before getting post-op x-rays, sometimes this occurs immediately prior to discharge, making it difficult to ensure the quality of the x-ray.

In situations where the post-op x ray is found to be inadequate but the patient has already been discharged, it is permissible to retake the x-ray at the 2nd week follow-up visit and consider those x-rays as the control. While this situation is not ideal, it is an appropriate back-up option in case the immediate post-op x-rays are inadequate.

For further information on x-ray quality control, refer to the addendum at the end of this document.

5.4 Wound Measurement and Classification

A measurement of the wound is to be done in the operating room. Specifically, it should be taken after the patient receives anesthesia and the temporary splint/bandages have been removed but just before surgical debridement. The wound should be measured using a centimeter ruler (rather than visually approximated) and recorded onto REDCAP.

Only the maximum dimension of the wound (the longest length possible) needs to be recorded. This is irrespective of how the wound is oriented along the limb. The wound length should only include the part of the wound that is open (ignore any superficial abrasions that may be connected to the open part of the wound).

OTA Wound Classification

Classification of the wound is done using the OTA Wound Classification questionnaire (see REDCAP section). Wound classification is to be done after surgical debridement which allows the surgeon to fully assess the wound.

Wound Closure Status Check

After surgical debridement, the surgeon will assess the wound to see if the wound can be primarily closed. If the wound can be primarily closed, the patient will continue with the RCT Study.

If the wound cannot be primarily closed, the patient will be enrolled as a cohort study patient.

If the wound is found to be primarily closeable and came to MOI within 24 hours of injury, the patient will be funneled into the RCT study and randomized

5.5 Damage Control

After assessing the wound, the primary surgeon will need to determine if “damage control” using a temporary external fixator is necessary. This may be utilized in situations where the patient is hemodynamically unstable and needs quick stabilization of the tibia or requires another surgery that is more important. This option is available to the surgeon for both RCT and cohort patients. Furthermore, this option is available for RCT patients who are randomized to either a nail or an exfix.

If the surgeon decides to perform damage control, a temporary external fixator will be placed, and the patient will be allowed to recover in the ward with the definitive operation performed at a later date. The date of both the temporary exfix placement and the definitive operation will be recorded onto REDCAP. There is no set time limit or criteria for how long the temporary external fixator should remain on before the definitive treatment is to be conducted. The only standardized policy is that the definitive operation should take place in a timely manner after the clinical issue that warranted the temporary external fixator in the first place has been resolved.

5.6 Randomization

The following information applies only to patients who are eligible and enrolled in the RCT study. For cohort study patients, the primary surgeon is responsible for deciding which surgery is the most appropriate for the patient. This includes either nail or exfix and the number of proximal and distal interlocks or schanz screws.

After the surgeon has deemed that the patient’s wound can be primarily closed, the patient is ready to be randomized. Randomization will be done via the REDCAP module. The randomization allocation table utilizes a pseudo-random number generator from sealedenvelope.com and incorporates block randomization to maintain roughly equal distribution between the two groups throughout the study. The number of random allocations is set to 340 to account for additional patients beyond the 240 that is expected to be enrolled.

The patient will be randomized to receive either a hand-reamed SIGN intramedullary nail or locally available external fixator. Both modalities will be applied using standardized techniques.

5.7 Definitive Treatment

Nail: It is up to the surgeon’s discretion as to the appropriate size of the nail. A total of 4 screws will be placed – 2 proximal and 2 distal. These decisions will be recorded on REDCAP during the operation.

Exfix: Two Schanz screws will be placed proximally and two will be placed distally; only a single bar will utilized. The patient will be instructed on proper pin-care procedures at the time of discharge which involves pouring methylated spirit (alcohol) directly onto the pins twice daily until the exfix is removed. The patient will be discharged with bandages covering the wound, but the pin insertion sites will be left open to allow for proper ventilation and pin-care. The patient will be discharged with dressing covering the wound and pin sites. The exfix will remain on for 3 months. At the 3 month follow-up, the decision will be made to (1) remove ex-fix, (2) remove ex-fix and replace with cast, (3) delay exfix removal, or (4) other. Delayed removal or other will be submitted for adjudication review.

Wound Protocol

If the wound is dry at the 2 week wound check, the dressing will be removed. If the wound is still wet at 2 weeks, the dressing will be changed and the patient will be instructed to periodically revisit the hospital to change the dressing until the wound becomes dry.

Weight Bearing Protocol

All patients will be advised to be on toe-touch status for the first 6 weeks. Afterwards, the patient will be instructed to bear weight as permitted by pain.

Summary of Treatment Options

Primarily closeable?	->	No	->	Cohort Study
	->	Yes (Cohort) (+ damage control)	->	Temporary exfix
	->	Yes (Cohort) (no damage control)	->	Definitive operation
	->	Yes (RCT): Nail (+ damage control)	->	Temp exfix (then nail)
	->	Yes (RCT): Exfix (+ damage control)	->	Temp exfix (then exfix)
	->	Yes (RCT): Nail (no damage control)	->	Nail now
	->	Yes (RCT): Exfix (no damage control)	->	Exfix now

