Email: [contact]

1. Summary of Changes to Standard Operating Procedure

February 3, 2016 ([name])

Various items that required clarification arose after the first few weeks of the study. The following clarifications were agreed upon:

- **Damage Control:** Allowed (definitive treatment done within 2 weeks after first operation)
- **Exfix Pin-Care:** 2 weeks with dressing and BID pin wash with alcohol. Check at 2 week follow up. If dry, remove dressing. If discharge present, continue with dressing and additional evaluations before 6 weeks
- **Exfix Treatment:** 3 months then the following at surgeon's discretion to be documented in eval form (1) removal, (2) removal with cast, (3) delayed exfix removal, or (4) other. Delayed exfix removal or other will be submitted for adjudication review
- **Antibiotics:** 3 options at surgeon's discretion with (1) CTX, (2) CTX + gentamycin, (3) CTX + gentamycin + metronidazole
- **Weight Bearing Protocol (all patients):** 6 weeks toe touch then at surgeon's discretion
- **Nurses:** 2 per week (number of patients will increase next Saturday)
- **# IM Nail Interlocks:** 4 total on all nailed patients (2 prox, 2 distal)
- **Continue with study without interruption:** Yes
- **Cohort Study:** Will now include non-primarily closeable patients (we will attempt to contact the patients who came in since the start of the study)

There was also a patient "borderline" fracture who will be included and followed-up. We have made a note and can exclude during data analysis if necessary.

February 13, 2016 ([name])

Following the presentation of an open tibia patient approximately 3 days after their injury, a discussion occurred regarding whether or not an upper limit would be set for patients in the cohort study who present >24 hours post-injury.

- ➔ It was decided that there would be no upper limit.

April 6, 2016 ([name])

- ➔ It was decided that exfix patients who receive a cast will have the cast paid for by the study since it is a complication of their randomization (and not part of their typical treatment plan)
- ➔ [name] will send out a revised budget

April 10, 206 ([name])

[name] noticed during his site visit to MOI that there was underreporting of pin tract infections in the external fixation group. Previously, the question, "are the schanz pin tracts infected?" would only

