Any IPSILATERAL UPPER extremity injuries?			reset
Any CONTRALATERAL UPPER extremity injuries?			reset
Describe other ipsilateral lower extremity injuries			Expand

Injury Severity Score			
	Yes	No	
Head/Neck (+ Cervical Spine)			reset
Face (+ Facial Skeleton, Nose, Mouth, Eyes, Ears)			reset
Chest			reset
Abdomen (+ Lumbar Spine)			reset
External			reset
Describe head/neck injuries			Expand

5. Antibiotics Check

a. Record any additional antibiotics that were given in the ward and whether or not all the courses of antibiotics the patient was started on were properly completed (all doses were given on time)

Antibiotics Check

Did the patient get started on any other antibiotics while in the ward besides the ones that have already been recorded?

Yes
 No

* must provide value reset

What other antibiotics did the patient receive?

- Type of antibiotic
- Dose
- Timing

Expand

Were all antibiotic courses administered on time and completed?

Yes
 No

This is a key study question

* must provide value reset

Describe which antibiotics were not administered on time or completed.

Expand

Standard Study Antibiotics Regiment

- None or Mild Wound Contamination: Ceftriaxone (1g every 24hr for 2 days)
- Moderate: Ceftriaxone (as above) + Gentamycin (80mg every 12hr for 2 days)
- Severe or High-Risk: Ceftriaxone + Gentamycin (as above) + Metronidazole (500mg every 8hr for 2 days)

b. Pin care information should be given to patients who have an exfix. The protocol is to pour methylated spirited onto the pin 2x a day

Discharge

Has the patient received proper exfix pin care information?

Yes
 No

reset

Please instruct the patient on proper pin-care (pour methylated spirit onto the pin 2x a day)

Afterwards, change the answer to the above question to "Yes".

Has a follow-up schedule been generated for the patient?

* must provide value Yes
 No

reset

Please save this form as "Incomplete" and generate a follow-up schedule for the patient. Afterwards, change the answer to the above question to "Yes".

Time and Date of Discharge

* must provide value Insert date and time by clicking on the calendar image above

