Is the patient able to perform the walking speed test? 
reset
 
  Yes  No 
		
Walking Speed Test #1 (Seconds): 
Time to walk 4 meters (in seconds)
		
Walking Speed Test #2 (Seconds): 
Time to walk 4 meters (in seconds)
		
Averaged walking speed test time 
View equation
		

5. Complications

- a. Properly recording complications is critical for the study because our end goal is to compare complication and reoperation rates between the two groups.
- b. Exfix patients will have additional questions appear related to schanz pin tract infections

Exfix Questions

Has the patient been performing proper pin-care with spirit 2x a day?

Yes
 No

reset

Please inform the patient about the importance of proper pin care

What is the plan for the exfix?

(Removal at 3 months with or without cast applied is standard procedure)

Exfix removal at 3 months
 Exfix removal AND a cast will be applied
 Delayed exfix removal
 Other (early removal, conversion, etc.)

reset

This exfix plan is not standard. Please report this as a complication in the "Complications and Review" Form

Are the Schanz pin tracts infected?

Yes
 No
 N/A (Exfix already removed)

reset

How many pins are infected?

1 2 3 4

reset

Pin tract infection level (and corresponding treatment plan):

0 - Normal (requires weekly pin care)
 1 - Inflamed (requires daily pin care)
 2 - Serous discharge (requires antibiotics)
 3 - Purulent discharge (requires antibiotics)
 4 - Osteolysis (requires removal of pin)
 5 - Ring Sequestrum (requires debridement)

reset

Since surgery is required to fix the schanz pin infection, please record the details on the "Complications" Form

- c. If the patient has a medical or surgical complication, record "Yes" and proceed to the "Complications and Review" form. That is where additional information will be recorded.
 - i. A pop-up warning will appear if a patient has had a complication recorded and is coming back for follow-up. This is to enable us to be up to date with complications.

Complications

Does the patient have any complications? These can include:

- Infection
- Wound problems
- Nonunion/malunion
- Hardware failure
- Medical problems

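### Protocol section 5.7 gives two incompatible discharge instructions for external-fixation pin sites, left open and covered; the follow-up form's grade labels also disagree with its pin-care frequency

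*Protocol*

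**What the plan says.** **Pin sites at discharge.** In the external-fixation paragraph of section 5.7, one sentence has the wound bandaged but adds that "the pin insertion sites will be left open to allow for proper ventilation and pin-care". The sentence after it reads "The patient will be discharged with dressing covering the wound and pin sites".

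**Frequency of pin care.** Section 5.7 describes the procedure as "pouring methylated spirit (alcohol) directly onto the pins twice daily until the exfix is removed". Section 6.4 tells the person completing the discharge form: "The protocol is to pour methylated spirited onto the pin 2x a day". The follow-up form in section 6.5 asks "Has the patient been performing proper pin-care with spirit 2x a day".

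**Grade labels.** The same follow-up form has a 0-to-5 item headed "Pin tract infection level (and corresponding treatment plan". Its lowest option is "0 - Normal (requires weekly pin care", and grade 1 (inflamed) is labelled as needing daily care.

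**Background.** The February 3, 2016 entry in the summary of changes records, for external-fixator pin care, "2 weeks with dressing and BID pin wash with alcohol. Check at 2 week follow up. If dry, remove dressing". If there is discharge, the dressing continues with further checks before six weeks.

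**The concern.** The protocol doubles as the working procedure for coordinators, nurses and ward staff. A patient going home with a fixator must receive one instruction about the pin sites, and section 5.7 gives two that exclude each other.

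The stakes are the care of patients in one arm and the interpretation of one secondary outcome. Section 4.1 defines superficial infection so that it includes pin tract infection, and the second specific aim compares superficial infection between the arms. If the sites are handled in different ways, a reader of the results will not know which pin care the external-fixation arm's infection rate reflects.

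The form labels raise a smaller version of the same problem. A clinician who grades a site and reads the label as the plan sees a lower frequency than the patient was given at discharge.

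**Working it through.** No stated figure in the plan depends on this point, so the check sets the passages side by side.

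1. **Do the two sentences in 5.7 describe the same thing?** Yes. Both concern the external-fixation patient at discharge. The first separates the wound (bandaged) from the pin sites (open). The second puts both under the dressing. No difference in timing, patient group or wound state is given that would let both apply.

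2. **Does anything else in 5.7 settle it?** No. The Wound Protocol paragraph says when a dressing comes off or is changed, but it refers only to the wound. The twice-daily alcohol instruction does not settle it either, because the February 2016 entry combines that frequency with a dressing.

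3. **Does the summary of changes settle it?** It describes a dressing for two weeks, with removal if dry. That makes it plausible that one sentence in 5.7 is an unedited remnant. The contradiction does not rest on comparing the log with the text, because it lies wholly inside current section 5.7. That section does not say which sentence stands.

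4. **Frequency, in applications per week:**
   - Section 5.7, section 6.4 and the pin-care question in 6.5: 2 × 7 = 14. Only section 5.7 adds that this runs until the fixator is removed.
   - Section 6.5, grade 1 label: 1 × 7 = 7.
   - Section 6.5, grade 0 label: 1.

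   Taken literally, the labels call for one half and one fourteenth of the frequency in 5.7.

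5. **How many patients?** Section 5.6 expects 240 enrolled, with block randomization to roughly equal arms: 240 / 2 = 120 on external fixation. That count suits the discharge sentence. It does not suit the grade labels, which depend on the state of each site.

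6. **How common is the affected outcome?** The pilot (section 2.3) reports superficial infection in 12 external-fixation patients: 12 / 26 = 46.2%, or 12 / 24 = 50.0% if only the 24 followed patients are counted. This shows that the outcome is frequent. It says nothing about what drives it.

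7. **Does it reach the primary outcome?** Section 4.1 excludes bedside irrigation and debridement for superficial pin tract infection. On the follow-up form, grades 4 and 5 (pin removal, debridement) are sent to the complications form as needing surgery, and section 5.10 sends complications requiring reoperation to adjudication. A route to the primary outcome therefore exists for severe cases, but the main exposure is the secondary outcome.

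**The case against.** The strongest reply is that this is an editing slip with an evident history. The February 2016 entry sets out one coherent sequence. On that entry, the dressing question covers about the first two weeks of a planned three-month fixator period for dry sites, and longer only where there is discharge. Every instruction addressed to the patient is twice daily. The weekly and daily wording appears only as answer options on a data form. The severity item comes after a question on whether the tracts are infected and another on how many pins are, so grade 0 may seldom be chosen; the branching is not stated, so that is an inference.

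Much of this stands. The frequency conflict is the weaker part, because a member of staff would have to set aside several consistent statements, one of them on the same form, to act on the weekly label. It is not empty, since the form itself calls the labels a treatment plan and words them as requirements. The history of the discharge sentences does not remove their conflict: a nurse reading section 5.7 still finds two instructions.

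A reader might also cite the statement in section 5.6 that both modalities use standardized techniques, and infer that the protocol breaks its own promise. In context that statement concerns applying the nail or fixator. It does not speak to pin hygiene after discharge.

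**Conclusion.** The contradiction in section 5.7 is real and needs no assumption beyond reading two adjacent sentences. The mismatch between the form labels and the twice-daily instruction is also real but secondary. Together they affect the written care instructions for one arm, about 120 patients if enrollment reaches 240 and allocation is even, and one secondary outcome.

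Two stronger readings are tempting and unsupported. The first is that the pin tract infection rate depends on which sentence staff follow. The documents give no infection rate by dressing status or care frequency, and do not show that staff acted differently from patient to patient. The pilot's 46.2% shows only that superficial infection is common. The second is that the primary comparison is compromised. Bedside treatment of superficial pin tract infection is excluded from the primary outcome, and nothing in the documents indicates how many severe cases would reach adjudication through this route. The size of any effect is therefore unknown. The case for correction rests on clear instructions for patient care and an interpretable secondary outcome.

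**What to change.** - In section 5.7, reconcile the two sentences so that one discharge instruction for the pin sites remains, and check that it agrees with the rest of the pin-care text.
- On the follow-up form in section 6.5, either make the grade 0 and grade 1 labels agree with the frequency in 5.7, or mark the scale as a grading description only and remove its description as a treatment plan.
- Inform ward, clinic and research staff of the single instruction.

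Which pin-care rule applies is for the clinical investigators to decide. The cost is one sentence deleted or reworded, a change to two form labels or the item's heading, and a notice to staff. Sample size, randomization and outcome definitions are unaffected.
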